#### 8.2. Registration

Participants must be registered centrally with the ICR-CTSU once written informed consent has been provided and study eligibility has been confirmed.

The eligibility and registration checklists should be completed, and sites should then call ICR-CTSU:

Patients should be registered by calling ICR-CTSU on:

#### [name]

The following information will be required for registration:

Name of hospital, consultant and person registering patient

Confirmation that patient has given written informed consent for study participation (and whether there are any aspects of the study the patient has not consented to eg. optional sub-studies)

Confirmation that patient is eligible for the study by completion of the eligibility checklist

Patient's full name, date of birth,

Patient's PRIMETIME pre-screening number

Clinicopathological data required for IHC4+C calculation:

- o tumour grade,
- tumour size (mm),
- o confirmation that the patient is node negative (as per the definitions in eligibility criteria),
- o patient age,
- o planned endocrine therapy type,
- o ER score (H score), PR score (% positivity), HER2 status.

Using the above information, ICR-CTSU will calculate the patient's IHC4+C score and provide this score to the participating site.

ICR-CTSU will return confirmation of registration, within 24 hours. Confirmation will include:

- a summary of the information provided by the centre used to perform the IHC4+C calculation
- o confirmation of the patient's IHC4+C score
- o recommended directed treatment informed by IHC4+C score. Patients who are categorised to be in a 'very low' risk group will be directed to avoid radiotherapy. All other patients will be directed to receive radiotherapy according to standard practice (see Study Treatment section below for a summary of risk categories and their directed treatment recommendation).
- Confirmation of the patient's unique Study ID

Research centres are encouraged to discuss the risk categorisation with the patient to ensure any questions relating to this result are fully answered before proceeding with biomarker-directed treatment.

Patients categorised to be in the 'very low' risk group still have the option to have radiotherapy and likewise those in the higher risk groups still have the option not to have radiotherapy. PRIMETIME will record all registered patients irrespective of whether they deviate from the protocol-directed treatment recommendation, but their final treatment decisions must be recorded and follow up must be according to the treatment the patient receives.

#### 8.3. Baseline

For all registered patients:

- Baseline characteristics and medical history should be recorded on the relevant PRIMETIME eCRFs.
- An archival tissue sample should be identified and requested from the local pathology department. This sample should be an FFPE block of primary tumour collected at surgery.

#### 8.4. IHC4+C directed treatment

The recommended need for radiotherapy will be directed by the biomarker read out from IHC4+C calculation.

Patients categorised to be in the 'very low' risk group, as confirmed at study registration, will be recommended for avoidance of radiotherapy.

Patients categorised to be in the 'Low', 'Intermediate' or 'High' risk groups, as confirmed at study registration, will be directed to receive radiotherapy according to the PRIMETIME radiotherapy planning pack.

The risk categories are defined in the table below:

Assigned risk category	Directed treatment			
Very low Avoidance of radiotherapy (Surgery only)				
Low	Radiotherapy			
Intermediate	Radiotherapy			
High	Radiotherapy			

For all patients, regardless of risk category, all other anti-cancer treatments (for example endocrine therapy) should be administered and managed according to local practice.

For patients receiving radiotherapy, data on radiotherapy planning and delivery (including DICOM data) should be recorded in the relevant PRIMETIME eCRF.

## 8.5. Follow-up

Follow up of patients will vary according to whether or not the patient receives radiotherapy. If treatment deviates from that directed at registration the follow up schedule should proceed according to the treatment the patient ultimately *receives*.

#### 8.5.1. Patients who do not receive radiotherapy

- Patients should have an annual mammogram for 10 years. (i.e. mammograms in line with local practice for the first 5 years, patients have annual mammogram for 5 additional years)
- Patients should attend clinic visits according to local practice.
- ICR-CTSU will contact research sites annually to request an update on patient status. Reasonable efforts should be made to contact patients annually for ten years.
- Information collected at follow up visits and the annual mammogram should be recorded in the PRIMETIME eCRF.

#### 8.5.2. Patients who receive radiotherapy

- Patients should have annual mammograms according to local practice.
- Patients should attend clinic visits according to local practice.
- ICR-CTSU will contact research sites annually to request an update on patient status. Reasonable efforts should be made to contact patients annually for ten years.
- Information collected at follow up visits and the annual mammogram should be recorded in the PRIMETIME eCRF.

As described above, it is intended that research sites will follow up all patients annually for ten years. Over the course of the study, the study team aim to transfer the provision of long term follow up data from research sites to routine data sources where the patient has provided consent to do so and where the required data point is available. This is intended to relieve the burden of long term follow up on research sites, and as a move towards this, data collection in the eCRF for patients where no disease event has occurred is minimal.

#### 8.5.3. Follow up from routine data sources

Written informed consent should be sought from patients for the ICR-CTSU team to access data in their national medical records, currently held by Public Health England and the Health and Social Care Information Centre on their health status. The relevant data sources include the Cancer Services and Outcomes Dataset (COSD), the National Radiotherapy Dataset (RTDS), the Systemic Anti-Cancer Therapy Dataset (SACT), the Hospital Episodes Statistics (HES), the ONS mortality file, equivalent databases in the devolved nations and any other informative UK registries. It is likely that some level of data mining will be required to examine hospital episodic activity as a proxy indicator.

Prospective collection of routine data will be requested from these sources at regular intervals for patients who enter the main study and those who are pre-screened, but do not subsequently enter the main study (ie. who consent for Ki67 research testing).

#### 8.6. Procedure at disease recurrence/relapse or diagnosis of new primary cancer

If a patient has a local or distant relapse, new breast primary cancer the following procedures should be followed:

- Routine clinical, histological and imaging information should be collected on the disease relapse and entered into the PRIMETIME eCRF.
- Tumour tissue collected from the diagnostic biopsy and/or any applicable surgical procedures should be provided to the study central laboratory.
- The patient should be treated accordingly to local protocol for relapse / new primary cancer. For those not receiving radiotherapy at initial diagnosis, further breast conserving surgery and radiotherapy could be considered.

#### 8.7. Discontinuation from Follow-up

#### If a patient no longer wishes to attend follow up visits:

If a patient chooses to withdraw from further follow-up, centre personnel should confirm whether they simply no longer wish to attend study follow up visits, but are happy for the information to be collected from other sources or whether the patient has withdrawn consent for further information to be sent to the ICR-CTSU. ICR-CTSU should be informed via completion of the relevant forms in the eCRF.

#### If a patient no longer wants their data to be sent to ICR-CTSU:

In the very rare event that a patient requests that the ICR-CTSU can no longer collect information on them from routine data sources, the implications of this should be discussed with the patient first to ensure that this is their intent and, if confirmed, ICR-CTSU should be notified in writing.

# 8.8. Schedule of Events/Assessments

Visit/Assessment	Pre-Screening	Screening (post surgerγ)	Registration	Baseline (prior to commencing radiotherapy)	Radiotherapy delivery	Data collection from routine follow up clinics	Annually – years 1-10	Disease Relapse
Informed consent (research testing)	Х							
Pre-screening request submitted to ICR-CTSU	X							
5 slides from diagnostic biopsy sent to central lab	Х							
Central lab perform Ki67 testing, feedback result to ICR-CTSU	Х							
Informed consent (main study)		Χ						
Completion of IGS Questionnaire (either A or B, see Appendix A5) 		Χ						
Study eligibility checklist completed		Χ						
Study registration form submitted to ICR-CTSU			Χ					
ICR-CTSU confirms IHC4+C score and directed treatment			Χ					
Discuss IHC4+C score and directed treatment with patient				Х				
Baseline characteristics / medical history				Х				
FFPE block from primary tumour identified				Х				
Radiotherapy planning and DICOM data collection 								
Radiotherapy according to standard care					X 			
Radiotherapy delivery data collection						X 		
Concomitant anti-cancer treatment data collection							Χ	
Mammogram						Х	$X^4$	
Access to information from routine follow up						Х		
Disease status						Х	Х	
Routine clinical, histological and imaging information 						Х		Х
FFPE block from site of disease relapse identified								Х

#### Footnotes

- 1. Radiotherapy plans may be collected electronically by the QA team if requested by the PRIMETIME study team, TMG or IDMC based on the recurrence rates seen in the study.
- 2. For patients categorised to be in the 'low', 'intermediate' or 'high' risk groups according to the IHC4+C score calculated in the PRIMETIME study. Or for patients categorised to be in the 'very low' risk group directed to avoid radiotherapy, but who decide not to follow the study recommendations, such patients would also receive radiotherapy according to standard care.
- 3. At the first follow up following completion of radiotherapy
- 4. Patients not receiving radiotherapy should have an annual mammogram for 10 years. Patients receiving radiotherapy should have annual mammograms according to local practice.
- 5. At any time during the study
- 6. The questionnaire needs to be given to the patient immediately AFTER they have decided whether or not to participate in PRIMETIME main study.

#### 9. RADIOTHERAPY

For patients directed to receive radiotherapy, standard of care radiotherapy should be delivered.

#### 9.1. Radiotherapy Treatment Timelines

Radiotherapy should commence within 8 weeks following breast conserving surgery and ideally within 31 days following breast conserving surgery as recommended by NICE. Occasionally, this will need to be delayed to allow treatment for breast infection or persistent seroma.

Radiotherapy is not thought to be effective if there is a long delay between surgery and radiotherapy. The PRIMETIME patient information sheet states "If you agreed not to have radiotherapy at the start of the study, you can change your mind up to 8 weeks after your surgery. Radiotherapy is not thought to be as effective if there is too long a delay between surgery and radiotherapy, so after this time you may not be able to receive radiotherapy".

The patient's treatment in this scenario is at the investigator's discretion.

#### 9.2. Radiotherapy Planning and Delivery

Radiotherapy planning and delivery should be carried out in accordance with the best current routine practice, as exemplified in the Fast Forward planning and delivery guidelines.

#### 9.3. Supportive Care Guidelines

All required supportive care should be delivered according to local practice.

#### 9.4 Radiotherapy Quality Assurance (QA)

A quality assurance program will be instigated to ensure the safety and consistency of radiotherapy delivery at participating sites. For further information please see Appendix A2.

#### 10. CONCOMITANT ANTI-CANCER THERAPY

For all patients, regardless of whether they receive radiotherapy or not, all other anti-cancer therapy should be delivered according to standard care. As per the inclusion criteria, patients must have been recommended 5 or more years of endocrine therapy. At the time of registration into the study investigators must deem the patient to be able to comply with the duration of the endocrine therapy and any other required anti-cancer therapies prescribed.

Compliance with endocrine therapy (ie. continuation with prescribed treatment) should be followed up by the research team at the time of annual follow up and recorded in the PRIMETIME eCRF.

Details of other anti-cancer therapies should be recorded in the PRIMETIME eCRF.

#### 11. SAFETY REPORTING

#### 11.1. Definitions

#### **Adverse Event (AE)**

An AE is any untoward medical occurrence in a patient administered a research procedure; the event does not necessarily have a causal relationship with the procedure.

The recording of AEs not meeting the definition of serious is not required in PRIMETIME.

#### **Serious Adverse Event (SAE)**

An SAE is any untoward medical occurrence that:

results in death,
is life-threatening
requires hospitalisation or prolongation of existing inpatients' hospitalisation
results in persistent or significant disability or incapacity
is a congenital anomaly or birth defect

For patients receiving radiotherapy, the SAE reporting period should commence at study registration and end 30 days after radiotherapy is complete.

For patients not receiving radiotherapy the equivalent SAE reporting period is considered to commence at study registration and cease after 17 weeks. This is considered equivalent to the reporting period for those receiving radiotherapy, as radiotherapy must commence within 8 weeks of breast conserving surgery, will last a maximum of 5 weeks and the SAE reporting period continues for 30 days after the end of radiotherapy.

Important adverse events that are not immediately life-threatening or do not result in death or hospitalisation but may jeopardise the subject or may require intervention to prevent one of the other outcomes listed in the definition above, may also be considered serious.

Recurrence of the indicated disease, new primary cancers, death due to progression of the indicated disease and planned/elective hospital admissions are not considered SAEs.

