#### 6. PRE-SCREENING - Ki67 RESEARCH TESTING

Pre-operative identification of patients likely to meet PRIMETIME eligibility criteria, allows sufficient time for pre-screening Ki67 testing prior to post-operative study registration. Patients meeting the pre-screening criteria and who provide written informed consent to PRIMETIME pre-screening will be asked to donate five slides taken from their diagnostic biopsy for central testing of Ki67.

The patients who should be approached for pre-screening are those who appear likely to be eligible for PRIMETIME based on the information known prior to surgery. Such patients will be those:

- o who are over 60 (or younger than 60 if they are post-menopausal and have co-morbidities that imply a high risk of radiotherapy toxicity (e.g. significant cardiovascular disease with left sided breast cancer)).
- o with no clinical evidence of high risk disease,
- o who are ER positive,
- o who are tested for PR
- who are HER2 negative (or whose HER2 result is awaited),
- o with grade 1 or 2 tumours,
- who are pre-operatively assessed as node negative,
- With a tumour estimated to be ≤2cm in size

Patients should be approached as early as possible in their treatment pathway to allow ample time for Ki67 testing before post-operative registration into the study. A minimum of 2 weeks should be allowed to complete Ki67 testing.

The patient's Ki67 result will be provided by the testing laboratory to ICR-CTSU and used to calculate the IHC4+C score for patients who subsequently register for the PRIMETIME study. For patients registering into the PRIMETIME study, their IHC4+C score (and Ki67 result) will be provided to centres at the time of registration (post surgery). For patients who provide tissue samples for Ki67 testing but who do not go on to register into the main PRIMETIME study, ICR-CTSU will provide the IHC4+C score to centres. Centres will need to provide the additional clinicopathological data required for IHC4+C calculation for the score to be calculated (see study guidance notes for more information on requesting this). Please note, we strongly advise that the IHC4+C is used in its entirety rather than the Ki67 score in isolation.

There will be a dynamic process throughout the study whereby centres may be able to transfer to local Ki67 testing subject to protocol amendment and once the relevant quality control checks have been carried out.

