#### 7. SCREENING FOR PRIMETIME STUDY

Please refer to the study flow diagram on p.X for a summary of the required procedures at each applicable timepoint.

After surgery and discussion at the multi-disciplinary team meeting, it will be possible to identify suitable candidates for PRIMETIME.

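### The 17-week SAE window for women not irradiated is called equivalent to the radiotherapy window, but it is summed from surgery and run from registration

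*Protocol*

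**What the plan says.** Protocol section 11.1, under the definition of a serious adverse event, sets two reporting windows that open on the same day but close by different rules. For irradiated women: "For patients receiving radiotherapy, the SAE reporting period should commence at study registration and end 30 days after radiotherapy is complete". For the others: "For patients not receiving radiotherapy the equivalent SAE reporting period is considered to commence at study registration and cease after 17 weeks". The reason given for treating these as equivalent is that "radiotherapy must commence within 8 weeks of breast conserving surgery, will last a maximum of 5 weeks", after which "the SAE reporting period continues for 30 days after the end of radiotherapy".

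Section 9.1 also counts the start of radiotherapy from surgery. It repeats the 8-week limit as a recommendation, adds a target of "ideally within 31 days following breast conserving surgery as recommended by NICE", and accepts that infection or a seroma will sometimes push the start back.

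Registration comes after surgery. Section 6 explains that identifying women before the operation "allows sufficient time for pre-screening Ki67 testing prior to post-operative study registration". Section 7 says: "After surgery and discussion at the multi-disciplinary team meeting, it will be possible to identify suitable candidates for PRIMETIME". Sections 3 and 16.3 describe the same order. No section gives the time from surgery to registration.

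**The concern.** Two features make the windows unequal. First, the clock: the 8-week term is measured from surgery and the other two terms are added on to it, so the total is a time since surgery. It is then applied from a later date. Second, the total takes the latest permitted start and the longest course and gives that ceiling to every woman not irradiated, while an irradiated woman's window closes 30 days after her own course ends.

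Both features lengthen observation in the omission cohort. Section 11.1 does not ask for non-serious events to be recorded, so SAEs are the only events collected on adverse-event forms, and it defines the study intervention as the omission of radiotherapy. Background hospital admissions in mostly older women accrue with time under observation. If SAE counts or percentages were set side by side, on the strength of windows that the protocol calls equivalent, the omission cohort would tend to look worse simply because it was watched for longer.

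**Working it through.** **Inputs**

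- From section 11.1: latest start 8 weeks = 56 days after surgery; longest course 5 weeks = 35 days; tail 30 days; fixed window 17 weeks = 119 days from registration.
- From section 9.1: target start 31 days after surgery.
- Assumed: gap g from surgery to registration, 7 to 28 days.

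**The plan's own figure.** 56 + 35 + 30 = 121 days = 17.3 weeks. This reproduces the stated 17 weeks (119 days) apart from a 2-day rounding. The addition is right; what is wrong is where it is counted from.

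**Radiotherapy window on the registration clock.** With a start s days after surgery and a course of d days, the window is s + d + 30 - g.

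- Longest case within the limits (s = 56, d = 35): 121 - g days. The excess of the fixed window is 119 - (121 - g) = g - 2 days, which is positive whenever registration is more than 2 days after surgery.
- Start at the target (s = 31, d = 35): 96 - g days. The excess is 119 - (96 - g) = 23 + g days.

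| g (days, assumed) | Longest in-limit window | Excess of 119 | Ratio | Window, 31-day start and 5-week course | Excess of 119 | Ratio |
|---|---|---|---|---|---|---|
| 7 | 114 | 5 | 1.04 | 89 | 30 | 1.34 |
| 14 | 107 | 12 | 1.11 | 82 | 37 | 1.45 |
| 21 | 100 | 19 | 1.19 | 75 | 44 | 1.59 |
| 28 | 93 | 26 | 1.28 | 68 | 51 | 1.75 |

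Each day taken off the course adds one day to the excess. The last row of the 31-day column is an edge case, because it leaves only 31 - 28 = 3 days between registration and the start of radiotherapy.

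**When the order reverses.** With a 5-week course, the irradiated woman's window reaches 119 days when s = 119 - 35 - 30 + g = 54 + g. That is day 61, 68, 75 or 82 after surgery for g = 7, 14, 21 or 28. All of these are later than day 56, so they require a delay of the kind that section 9.1 accepts.

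**The case against.** The best defence is that the 17 weeks is an administrative cut-off. The protocol shows its components, labels the course length as a maximum, and may mean only that the period covers the longest scheduled case. For case-by-case review of causality and expectedness, which is how section 11 uses SAEs, watching the omission cohort for longer is cautious rather than harmful. This stands as an argument for having a generous window. It does not support calling the windows equivalent, because 119 days overshoots even the longest in-limit case once registration is more than 2 days after surgery.

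Three stronger readings are tempting, and the documents do not support them.

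- *That the SAE results will mislead the monitoring committee or the final report.* No section plans a comparison of SAEs by cohort. Section 12.5 names ipsilateral invasive disease, the proportion at very low risk and non-compliance as the items to monitor. Section 11.6 reports related unexpected SAEs and safety concerns. Section 12.1 says the irradiated women are not a direct comparator. Deaths are also reported by sites to the end of the study, and linked hospital and mortality data are sought with consent, so serious events are not seen only through this window.
- *That the omission cohort is observed up to three times as long.* A ratio of 2.98 needs an assumed 1-week course, registration at day 28 and a start at day 31. The protocol gives no course length other than the 5-week maximum, and three days from registration to treatment is close to impossible.
- *That every woman not irradiated is observed longer than every irradiated woman.* Delayed starts can reverse the order for individuals.

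The window ratio is also only an approximate guide to the inflation of SAE percentages. It assumes uncommon events at a constant rate, and the inflation would be smaller if events cluster soon after surgery.

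**Conclusion.** The claim of equivalence is wrong as written. Its components describe a time since surgery, at the ceiling, and the protocol runs them from a later date. The direction, longer observation of the omission cohort as a group, follows from the text alone provided that radiotherapy stays within the stated limits and registration is more than 2 days after surgery. The size depends on the assumed gap of 7 to 28 days: a few days to just under four weeks against the longest in-limit case, and about one to one and three-quarter months against a start at the 31-day target with a full course.

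The consequence is limited. It touches only descriptive SAE summaries by cohort, should any be made, and those would be tilted against omission. Separately, section 11.1 states the 8-week start as an obligation while section 9.1 recommends it and accepts delay. The two sections must be reconciled, because the length of the window is derived from that limit.

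**What to change.** - In section 11.1, either remove the statement that the periods are equivalent, or count the surgery-based sum from the date of surgery. The second option corrects the clock only; the sum would still be a ceiling, and the text should say so.
- Reconcile sections 11.1 and 9.1 on whether the 8-week start is a fixed limit.
- State that any SAE summary by cohort will be given per patient-week of reporting time, or up to a common time point covered by both windows. The per-patient-week figure assumes a roughly constant rate. If events cluster soon after surgery, the common time point is the fairer choice.

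The cost is minor rewording and a small amount of extra analysis. The per-patient-week report needs no new data, because registration and end-of-radiotherapy dates already define each woman's window. Extending SAE reporting for irradiated women to match 17 weeks is not needed for this purpose.
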